5.1.1.9 Malignancy

The impact of BTK inhibition on the development of malignancies is not known; however, malignancies have been identified as a potential concern for immunomodulatory agents. Malignancies have been reported in patients with XLA, including lymphoreticular malignancies, gastric and colorectal adenocarcinoma, and squamous cell carcinoma of the lung.

All malignancies are considered AESIs for this study and should be reported to the Sponsor in an expedited manner as outlined in Section 5.2.3.

Guidelines for management of study treatment in the event of malignancies in patients are provided in Table 3. Please refer to the GDC-0853 Investigator’s Brochure for further details.

5.1.2 Management of Study Treatment in Patients Who Experience Specific Adverse Events

Guidelines for management of GDC-0853 in patients who experience specific adverse events are provided in Table 3. These guidelines do not cover all possible clinical scenarios; please consult the Medical Monitor when there are any questions about specific adverse events. For a potential dose reduction for other adverse events not listed in the table, please consult the Medical Monitor.

Table 3 Guidelines for Management of GDC-0853 in Patients Who Experience Specific Adverse Events

Event	Action to Be Taken ^a

Infection ^b
 
Serious infection or any infection requiring treatment with a prolonged oral or IV antimicrobial agent
 
Self-limited infections that require treatment
	
Withhold GDC-0853. Once the infection has resolved consult with Medical Monitor to discuss potential resumption of GDC-0853.
 
Withhold GDC-0853 during antimicrobial therapy.

Bleeding
	
Any Grade ≥ 2 bleeding event is considered an AESI and should be reported to the Sponsor in an expedited manner.
 
For Grade 3 or higher bleeding events or any serious bleeding event, withhold GDC-0853 and consult with the Medical Monitor. Once the bleeding event has resolved, consult with Medical Monitor to discuss the potential resumption of GDC-0853.


Neutropenia ^c
 
Grade 2: ANC >1000–$1500/\text{mm}^3$
 
Grade 3: ANC 500–$1000/\text{mm}^3$
 
Grade 4: ANC $<500/\text{mm}^3$
	
Maintain GDC-0853 dosing.
 
For the first occurrence of a Grade 3 neutrophil count decreased, withhold GDC-0853 and recheck the CBC in 7 days. If the neutrophil count has recovered to Grade 1 ($> 1500/\text{mm}^3$) or baseline, resume dosing at 200 mg BID unless there is a concurrent serious or Grade 3 infection. If still at Grade 2 (1000–$1500/\text{mm}^3$) and above baseline, consult with the Medical Monitor regarding further dosing instructions. If the Grade 3 neutropenia persists, discontinue GDC-0853.
 
For the second occurrence of Grade 3 neutrophil count decreased, withhold GDC-0853 and recheck the CBC in 7 days. If the neutrophil count has recovered to Grade 1 ($> 1500/\text{mm}^3$) or baseline, restart GDC-0853 at the lower dose of 200 mg QD for 1 week and recheck CBC after 1 week at the lower dose. If at Grade 2 (1000–$1500/\text{mm}^3$) and below baseline, consult with the Medical Monitor regarding further dosing instructions. If the Grade 3 neutrophil count persists, discontinue GDC-0853.
 
For the third occurrence of Grade 3 neutrophil count decreased, withhold GDC-0853 and confirm. If Grade 3 neutrophil count decreased is confirmed, discontinue GDC-0853.
 
Withhold GDC-0853 and confirm. If Grade 4 neutrophil count decreased is confirmed, discontinue GDC-0853.

Table 3 Guidelines for Management of GDC-0853 in Patients Who Experience Specific Adverse Events (cont.)

Event	Action to Be Taken a

Treatment emergent Grade 2 lymphopenia: lymphocyte count 500–800/mm³
 
Treatment emergent Grade 3 lymphopenia: lymphocyte count 200–500/mm³
 
Grade 4 Lymphopenia: lymphocyte count <200/mm³
	
Maintain study treatment dosing unless concurrent active infection or other clinical concern.
 
For the first occurrence of treatment emergent Grade 3 lymphopenia, withhold GDC-0853 and recheck CBC in 7 days. If lymphocyte count has recovered to >500/mm³ (Grade 2 or less severe), resume study treatment unless there is a concurrent serious or Grade 3 infection. If Grade 3 lymphopenia persists, discuss with the Medical Monitor.
 
For the second occurrence of Grade 3 lymphopenia, withhold GDC-0853 and recheck CBC in 7 days. If lymphocyte count has recovered to > 500/mm³ (Grade 2 or less severe), restart GDC 0853 at the lower dose of 200 mg QD for one week and recheck CBC. If still at < 800/mm³ (Grade 2 or more severe), consult with medical monitor regarding further dosing instructions.
 
For the third occurrence of Grade 3 lymphopenia, withhold GDC-0853 and confirm. If Grade 3 lymphopenia is confirmed, discontinue GDC-0853.
 
Withhold GDC-0853 and confirm. If Grade 4 lymphopenia is confirmed, discontinue GDC-0853.


Thrombocytopenia^d
 
Treatment Emergent Grade 1: PLT > 75,000/mm³
 
Treatment emergent Grade 2: PLT 50,000–75,000/mm³
 
Grade >3: PLT < 50,000/mm³
 
Grade 4: PLT < 25,000/mm³
	
In the absence of bleeding event(s), maintain GDC-0853 dosing.
 
For the first occurrence, in the absence of SLE flare, hold GDC-0853 and recheck CBC in 7 days. If platelet count has recovered to > 75,000/mm³ or to baseline, resume GDC-0853. If platelet count remains < 75,000/mm³, discuss with the Medical Monitor and consider reducing GDC-0853 dose to 200 mg QD.
 
For recurrence in the absence of bleeding events, discuss with the Medical Monitor and consider reducing GDC-0853 dose to 200 mg QD.
 
For the first occurrence, in the absence of SLE flare, hold GDC-0853 and recheck platelets in 7 days. If platelet count has recovered to baseline or above 75,000/mm³ (Grade 1), resume study treatment. If platelet count has recovered to 50,000–75,000/mm³ (and this is not baseline) in the absence of bleeding events, consider reducing GDC-0853 dose to 200 mg QD for 1 week and recheck platelets. If still at < 75,000/mm³, consult with Medical Monitor regarding further dosing instructions. For further occurrences or persistent Grade 3 treatment-emergent thrombocytopenia in the absence of SLE flare, after withholding or dose-reducing GDC-0853, and in the absence of bleeding events, discuss with the Medical Monitor or discontinue study treatment.
 
Discontinue GDC-0853.

Table 3 Guidelines for Management of GDC-0853 in Patients Who Experience Specific Adverse Events (cont.)

Event	Action to Be Taken a

Gastrointestinal effects
 
Nausea, vomiting, and/or diarrhea
	
Manage according to site institutional guidelines. Consider administration of GDC-0853 with food as possible mitigation strategy.
 
Consider reducing GDC-0853 dose to 200 mg QD and discuss with Medical Monitor.

Malignancy
 
Any malignancy (with the exception of non-serious local and resectable basal or squamous cell carcinoma of the skin)
	
Discontinue GDC-0853. Report event as an AESI to the Sponsor in an expedited manner.


Hepatotoxicity
 
Any AST or ALT $> 3.0\text{--}5.0 \times \text{ULN}$
 
AST or ALT elevation $> 3 \times \text{ULN}$ in combination with total bilirubin $> 2 \times \text{ULN}$, of which at least 35% is direct bilirubin, or clinical jaundice
 
Any AST or ALT $> 5 \times \text{ULN}$
	
Withhold GDC-0853 and consult with the Medical Monitor.
 
Discontinue GDC-0853 and consult with the Medical Monitor. Recheck liver laboratory tests, including AST/ALT, ALP, and total bilirubin, and CBC with differential (to determine eosinophil count), within 1 week (preferably within 72 hours). Assess patient for signs/symptoms of hepatic failure and for other causes of liver dysfunction (e.g. viral hepatitis, concomitant medications, etc.). Continue to monitor liver function tests until abnormalities resolve. Report Hy's Law cases as AESI to the Sponsor in an expedited manner.
 
Discontinue GDC-0853 and consult with the Medical Monitor. Recheck liver laboratory tests, including AST/ALT, ALP, and total bilirubin, and CBC with differential (to determine eosinophil count), within 1 week (preferably within 72 hours). Assess patient for signs/symptoms of hepatic failure and for other causes of liver dysfunction (e.g., viral hepatitis, concomitant medications). Continue to monitor liver function tests until abnormalities resolve. Elevations of AST or ALT of $> 5 \times \text{ULN}$ should be reported as AESIs to the Sponsor in an expedited manner.

Cardiovascular effects
 
Sustained (at least two ECG measurements > 30 minutes apart) QTcF that is > 500 msec and/or > 60 msec longer than the baseline value
	
Unless there is a clear alternative cause other than study drug, discontinue GDC-0853. ^e

Table 3 Guidelines for Management of GDC-0853 in Patients Who Experience Specific Adverse Events (cont.)

Event	Action to Be Taken a
Sustained absolute QTcF that is > 515 msec	Unless there is a clear alternative cause other than study drug, discontinue GDC-0853. ^e
An episode of torsades de pointes or a new ECG finding of clinical concern	Discontinue GDC-0853. ^e
Vascular Inflammation	
Vasculitis	Consult with the Medical Monitor.

AESI = adverse event of special interest; BID = twice a day; PLT = platelet count; QD = once a day; QTcF = QT interval corrected using Fridericia's formula; SLE = systemic lupus erythematosus; ULN = upper limit of normal.

- ^a Any patient who discontinues GDC-0853 should enter safety follow-up if possible.
- ^b Appropriate laboratory investigations, including, but not limited to, cultures, should be performed to establish the etiology of any serious infection.
- ^c Patients withdrawn from the study because of a reduced neutrophil count must be followed closely for signs of infection, with treatment as deemed appropriate by the investigator, and must have a repeat WBC count with differential performed weekly until the ANC is above 1000 cells/mm³ ($1.0 \times 10^9/L$). If the ANC does not return to above 1000 cells/mm³ ($1.0 \times 10^9/L$) within 2 months (or sooner if deemed necessary by the investigator), a hematology referral is recommended.
- ^d Patients withdrawn from the study because of a reduced platelet count must have a repeat platelet count weekly until the count is above 50,000 cells/mm³ ($50 \times 10^9/L$); additional management and treatment should be as deemed appropriate by the investigator.
- ^e In rare circumstances, it may be acceptable to resume GDC-0853, provided that any ECG abnormalities have resolved and that the patient is appropriately monitored. Clinical judgment should be applied and discussion with the Medical Monitor should occur.

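### Table 3 reverses the baseline comparison in the first-occurrence Grade 3 neutropenia row, and its Grade 2 bracket overlaps Grade 3 at exactly 1000/mm³ (minor)

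*Combined protocol and SAP*

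**What the plan says.** All of this is in Section 5.1.2, Table 3, neutropenia, unless stated otherwise.

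The event column puts Grade 2 at more than 1000 and up to 1500/mm³ (the entry opens "Grade 2: ANC >1000") and Grade 3 at 500 to 1000/mm³. Grade 2 alone leaves dosing unchanged. For Grade 3, the first and second occurrences have parallel text: withhold, recheck the blood count in 7 days, then choose among three outcomes.

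- **Recovered to Grade 1 (>1500/mm³) or to baseline.** First occurrence: "or baseline, resume dosing at 200 mg BID unless there is a concurrent serious or Grade 3 infection". Second occurrence: restart at 200 mg once daily for a week and recheck.
- **Grade 2.** First occurrence: the sentence opens "If still at Grade 2 (1000", closes the bracket at 1500/mm³ and continues "and above baseline, consult with the Medical Monitor regarding further dosing instructions". Second occurrence: the same bracket, then "and below baseline, consult with the Medical Monitor regarding further dosing instructions".
- **Still Grade 3.** First occurrence: "If the Grade 3 neutropenia persists, discontinue GDC-0853". The second occurrence has the same action.

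The Grade 3 thrombocytopenia row of the same table compares the count itself with baseline. Its resume step begins "If platelet count has recovered to baseline or above 75,000/mm", and its separate steps for a partly recovered count carry the condition "and this is not baseline) in the absence of bleeding events".

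Section 4.1.2 excludes patients with ANC below 1.5 × 10⁹/L (1500/mm³) at Week 44 of Study GA30044, with one repeat allowed. Appendix 1, footnote b, takes Day 1 values from Week 48 of that study.

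**The concern.** The two rows handle the same decision, yet the direction of the baseline comparison flips between them and nothing explains why. In the first row the flip also clashes with the sentence before it: a Grade 2 count that is above baseline has already recovered to baseline, and that sentence says to resume.

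The patient the referral is meant for is the one who has partly recovered, from Grade 3 to Grade 2, and is still below baseline. As printed, that patient has no branch. The only other line in Table 3 for a count of >1000–1500 is the Grade 2 line, which keeps dosing going, and a site looking for an applicable rule could turn to it. This is an operative dosing rule for an immunomodulator with infection listed as a potential risk, so it should give one answer.

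**Working it through.** The plan has no figure to reproduce here. The check treats the first-occurrence row as a set of rules and asks which of them each recheck value meets.

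**Inputs.** Let *b* be the baseline ANC and *r* the 7-day recheck, both per mm³. The grade limits and actions come from Table 3. A baseline of 1500 or more is inferred from the Week 44 entry limit. Because Day 1 values come from Week 48, a lower baseline is possible, so 1400 is also shown.

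**Rules, reading *baseline* as a count.**

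- Resume if *r* > 1500 or *r* ≥ *b*.
- Consult if *r* is in the row's Grade 2 bracket and *r* > *b* (as printed) or *r* < *b* (corrected).
- Discontinue if 500 ≤ *r* ≤ 1000 (Grade 3 in the event column).

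**As printed.** If *b* ≥ 1500, a Grade 2 recheck has *r* ≤ 1500 ≤ *b*, so *r* > *b* is impossible and consult is never reached. Any *r* above 1000, up to 1500 and below *b* meets no rule. If *b* is between 1000 and 1500, a Grade 2 recheck with *r* > *b* meets both resume and consult.

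**Worked cases, first-occurrence row.**

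| Baseline | Recheck | As printed | *Below* only | *Below* and >1000–1500 |
|---|---|---|---|---|
| 2200 | 1200 | no branch | consult | consult |
| 1400 | 1200 | no branch | consult | consult |
| 1400 | 1450 | resume and consult | resume | resume |
| 2200 | 1000 | discontinue | consult and discontinue | discontinue |

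The last line shows why the bracket matters. With *below* and the bracket 1000–1500, a recheck of exactly 1000 is Grade 2 by the action text and Grade 3 by the event column. The second-occurrence row already has that double match; changing only the word would bring it into the first row.

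**After both changes.** For any *b* > 1000 and *r* ≥ 500:

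- *r* from 500 to 1000: discontinue only, since *r* < *b* and *r* is outside the bracket.
- *r* above 1000 and up to 1500: resume if *r* ≥ *b*, otherwise consult.
- *r* above 1500: resume only.

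No value is left out and none is matched twice. Running the rules over baselines of 1001–4000 and rechecks of 500–1600 gave the same result.

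**The other reading.** Suppose *above baseline* means a worse grade than at baseline.

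| Row | Count reading | Grade reading |
|---|---|---|
| First occurrence (*above*) | fails, as shown | works for baselines above 1500 |
| Second occurrence (*below*) | works, except at exactly 1000 | fails |

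The second row fails on the grade reading because a Grade 2 recheck would have to be milder than baseline. Baseline would then be Grade 3 or worse (1000 or lower), against an entry limit of 1500. No single reading makes both rows work.

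**The case against.** **The fallback gives the same instruction.** The text above Table 3 says the guidelines are not exhaustive and sends questions to the Medical Monitor; Section 3.1 makes resumption after an interruption subject to the Medical Monitor's permission. A site following these would act in the no-branch cases as the corrected row directs. This stands, and it is why the point is minor. It does not make the row correct.

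**A grade reading rescues the first row.** The sentence speaks of being at Grade 2, and Section 5.5.1 refers to a baseline grade. The reading is possible, and the gap depends on rejecting it. But the preceding sentence compares the neutrophil count with baseline, and the grade reading moves the error to the second row. The platelet row gives further, weaker support for counts, since its steps differ.

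**Resume and consult can coexist.** If Section 3.1 applies, the overlap for baselines under 1500 is closer to redundancy than contradiction. This stands in part: the row sets the two out as alternatives, but the gap is the main fault.

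**The bracket concerns one exact value.** True, and a reader who applies the event-column definition of Grade 2 reaches discontinue. Still, the correction should not create a new double match in the first row. The lymphocyte rows share a boundary at 500/mm³ in the same way; that is a separate tidy-up.

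**The corrected rule is not clean for every baseline.** True: with a baseline of 1000 or lower (say 950, recheck 970), resume and discontinue would still both apply. The entry limit makes such a baseline very unlikely.

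**Conclusion.** The point holds, as a minor wording error in an operative safety rule. One of the two rows must be wrong on either reading, and the better-supported count reading puts the error in the first. There the referral branch cannot be reached at a baseline of 1500/mm³ or more, and the partly recovered patient has no specific instruction. The bracket mismatch is a smaller slip, confined to a recheck of exactly 1000/mm³.

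The conclusion assumes that *baseline* is a count, that recovery to baseline means *r* ≥ *b*, and that baseline exceeds 1000/mm³. The neutropenia row does not say which visit supplies baseline. The cases above are logical cases, not frequencies; the documents give no neutropenia rate in SLE. The rules for persistent counts below 1000, a third occurrence and Grade 4 are clear.

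**What to change.** In the first-occurrence Grade 3 row, replace *above* with *below* before *baseline*. In both the first- and second-occurrence rows, write the Grade 2 range as >1000–1500/mm³ to match the event column. Redefining Grade 3 in the event column as 500 to <1000 would also remove the overlap, but it would change the action at exactly 1000; aligning the action text is more direct.

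The cost is one word and two range brackets at the next amendment. No visit, procedure or analysis changes.

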5.2 SAFETY PARAMETERS AND DEFINITIONS

Safety assessments will consist of monitoring and recording adverse events, including serious adverse events and adverse events of special interest, performing protocol-specified safety laboratory assessments, measuring protocol-specified vital signs, and conducting other protocol-specified tests that are deemed critical to the safety evaluation of the study.

Certain types of events require immediate reporting to the Sponsor, as outlined in Section 5.4.

5.2.1 Adverse Events

According to the ICH guideline for Good Clinical Practice, an adverse event is any untoward medical occurrence in a clinical investigation subject administered a pharmaceutical product, regardless of causal attribution. An adverse event can therefore be any of the following:

- Any unfavorable and unintended sign (including an abnormal laboratory finding), symptom, or disease temporally associated with the use of a medicinal product, whether or not considered related to the medicinal product
- Any new disease or exacerbation of an existing disease (a worsening in the character, frequency, or severity of a known condition), except as described in Section 5.3.5.9.
- Recurrence of an intermittent medical condition (e.g., headache) not present at baseline
- Any deterioration in a laboratory value or other clinical test (e.g., ECG, X-ray) that is associated with symptoms or leads to a change in study treatment or concomitant treatment or discontinuation from study drug
- Adverse events that are related to a protocol-mandated intervention, including those that occur prior to assignment of study treatment (e.g., screening invasive procedures such as biopsies)

5.2.2 Serious Adverse Events (Immediately Reportable to the Sponsor)

A serious adverse event is any adverse event that meets any of the following criteria:

- Is fatal (i.e., the adverse event actually causes or leads to death)
- Is life threatening (i.e., the adverse event, in the view of the investigator, places the patient at immediate risk of death)

This does not include any adverse event that had it occurred in a more severe form or was allowed to continue might have caused death.

- Requires or prolongs inpatient hospitalization (see Section 5.3.5.10)
- Results in persistent or significant disability/incapacity (i.e., the adverse event results in substantial disruption of the patient's ability to conduct normal life functions)
- Is a congenital anomaly/birth defect in a neonate/infant born to a mother exposed to study drug
- Is a significant medical event in the investigator's judgment (e.g., may jeopardize the patient or may require medical/surgical intervention to prevent one of the outcomes listed above)

The terms "severe" and "serious" are not synonymous. Severity refers to the intensity of an adverse event (e.g., rated as mild, moderate, or severe, or according to NCI CTCAE;

see Section 5.3.3); the event itself may be of relatively minor medical significance (such as severe headache without any further findings).

Severity and seriousness need to be independently assessed for each adverse event recorded on the eCRF.

Serious adverse events are required to be reported by the investigator to the Sponsor immediately (i.e., no more than 24 hours after learning of the event; see Section 5.4.2 for reporting instructions).

5.2.3 Adverse Events of Special Interest (Immediately Reportable to the Sponsor)

AESIs are required to be reported by the investigator to the Sponsor immediately (i.e., no more than 24 hours after learning of the event; see Section 5.4.2 for reporting instructions). AESIs for this study include the following:

AESIs for GDC-0853

- Any serious infection, any infections requiring IV antimicrobials and any opportunistic infections
- Any bleeding event Grade 2 or above
- All malignancies
- A laboratory result of Grade ≥ 3 (i.e., $> 5 \times \text{ULN}$) AST or ALT elevation

AESIs for General Drug Development

- Cases of potential drug-induced liver injury that include an elevated ALT or AST in combination with either an elevated bilirubin or clinical jaundice, as defined by Hy's Law (see Section 5.3.5.6)
- Suspected transmission of an infectious agent by the study drug, as defined below:
Any organism, virus, or infectious particle (e.g., prion protein transmitting transmissible spongiform encephalopathy), pathogenic or non-pathogenic, is considered an infectious agent. A transmission of an infectious agent may be suspected from clinical symptoms or laboratory findings that indicate an infection in a patient exposed to a medicinal product. This term applies only when a contamination of the study drug is suspected.

5.3 METHODS AND TIMING FOR CAPTURING AND ASSESSING SAFETY PARAMETERS

The investigator is responsible for ensuring that all adverse events (see Section 5.2.1 for definition) are recorded on the Adverse Event eCRF and reported to the Sponsor in accordance with instructions provided in this section and in Sections 5.4–Section 5.6.

For each adverse event recorded on the Adverse Event eCRF, the investigator will make an assessment of seriousness (see Section 5.2.2 for seriousness criteria), severity (see Section 5.3.3), and causality (see Section 5.3.4).

